Quantitative assessment of caregiver strategies at baseline and follow-up will be via the JERI, and include: (1) scaffolding, (2) following in on a child's focus, and (3) caregiver affect. These items will be scored on a Likert scale by a trained rater, from video-recorded caregiver-child interactions. We hypothesize that 12 sessions of NDBI-informed caregiver coaching will result in significant changes in the frequency and quality of caregiver strategies. Quantitative data will be analyzed with a paired t-test (or Wilcoxon rank-sum test if appropriate) to evaluate the change in caregiver strategies pre versus post intervention. In order to account for the estimated 15% attrition, and ensure a final total sample size of 30 caregiver-child dyads in the ASD group for the pre-post phase of the study, 35 caregiver-child dyads will initially be recruited. We will thus have 90% power to detect a standardized effect size (Cohen's d) of 0.60 using a paired t-test, assuming we standardize the difference between pre and post scores to have mean 0 and standard deviation 1.

Qualitative caregiver perceptions of strategies used during caregiver-child interactions will be collected at follow-up. Interview scripts will be developed to facilitate a broader understanding of strategies that are culturally-relevant to South African caregivers. Individual interviews will be audio-recorded. Data will be transcribed verbatim and cross-checked for accuracy, and inductively analyzed via content analysis utilizing NVivo.

Aim 4: Adapt the NDBI caregiver coaching intervention and assessment of caregiver NDBI strategies for telehealth delivery in order to maintain services for young children with ASD impacted by COVID-19. Explore the acceptability, feasibility, and appropriateness of the adapted intervention and assessment approach.

Acceptability, feasibility and appropriateness of the telehealth approach will be evaluated. Views of multiple stakeholders: (1) Caregivers; (2) Early Childhood Development Practitioners; (3) Early Childhood Development Practitioner School Supervisors; and (4) NDBI supervisors will be assessed. Mixed methods will be used to understand the implementation process, and barriers and facilitators. Acceptability, feasibility, and appropriateness will be quantitatively assessed using the Acceptability of Intervention Measure (AIM), Intervention Appropriateness Measure (IAM), and Feasibility of Intervention Measure (FIM). In addition, acceptability, feasibility and appropriateness will be assessed qualitatively. The interview guide will be tailored to the stakeholder group and be informed by previous studies that have examined implementation barriers and facilitators during the implementation of a new treatment approach; including some of our previous work. At the interpretation phase, results will be triangulated. The process of conceptual triangulation will be followed.

Child social communication will be assessed with the Socialization and Communication standard scores from the Vineland Adaptive Behavioral Scale Third Edition (VABS-3). The VABS-3 will be administered telephonically at the baseline and follow up. We will evaluate pre-post change on the VABS-3 among dyads receiving the telehealth intervention using a paired t-test, under the null hypothesis of no change over time (in the case that the outcome data is heavily skewed, a Wilcoxon signed rank test will be used instead). Assuming the same standard deviations as the R21 pilot data (7.5 for Socialization and 8.3 for Communication), we will have 90% power to detect mean pre-post changes of at least 5.7 for Socialization and 6.3 for Communication.

Fidelity of intervention delivery, the degree to which programs are implemented as intended by program developers, is an important implementation outcome because it can moderate the impact of an intervention on targeted health outcomes. Pilot R21 data (n=10) suggests that South African caregivers can learn to implement core NDBI intervention principles. After 12 sessions: mean fidelity scores increased from 2.93 to 3.73. However, when interventions are adapted to fit a new target population, delivery setting, location or organization, maintaining intervention fidelity is of particular importance. As the intervention is adapted for delivery on a telehealth platform, fidelity is critical to monitor. Fidelity ratings can be completed from video-recordings of caregiver-child interactions. Caregiver child interactions will be recorded on the caregivers' Smartphone and uploaded to a HIPPA compliant Duke Box folder. Caregiver-child interactions will occur in the child's home, an authentic environment of the child, with every day materials that the child and caregiver are familiar with.

The Caregiver ESDM Fidelity Rating System provides a method for assessing fidelity; namely the degree to which a caregiver is using intervention principles in a joint activity routine with their young child. The 13 item rating scale includes ratings of performance on core intervention strategies from 1 to

5; where 1 represents a lack of an effective display of the practices specified, and 5 represents the best possible example of this teaching behavior. Fidelity of implementation of NDBI strategies will be manually coded by certified ESDM therapists at baseline, for each of the 12 intervention sessions, and at follow up. Mean fidelity scores (with SD) will be calculated across study participants in order to assess change in NDBI strategies. As with in-person intervention, we expect that caregivers will learn to implement core NDBI intervention principles after 12 intervention sessions. Pre-post change in the telehealth delivery group will be assessed using a paired t-test (or Wilcoxon signed rank test, as appropriate). Assuming the same standard deviation (0.6) as the R21 pilot data, we will have 90% power to detect a mean pre-post change of at least 0.5.

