Understanding the validity of NDBI targets across diverse populations will help match interventions to increasingly diverse populations in the U.S. In the U.S. African American and Hispanic/Latino children are diagnosed and access services at a later age as compared to Caucasian children. The majority of states have passed legislation that mandates insurance benefits for early intervention and there are increasing efforts to implement NDBIs in diverse communities. However, knowledge of how to tailor these interventions to diverse communities is incomplete. As such, the R21 aligns with NIMH Strategic Objective 4: To strengthen the public health impact of NIMH-supported research; and objectives of the Federal Interagency Autism Coordinating Committee Strategic Plan: To reduce disparities in early detection and outcomes for underserved populations.

Design & Procedures

The R21 will build on collaborations and infrastructure established in [name] NIMH K01. The K01 aims to adapt a caregiver coaching version of the Early Start Denver Model (ESDM), an NDBI and the first empirically-validated comprehensive intervention for toddlers with ASD, for implementation by non-specialists in South Africa. Following a significant amount of formative work and capacity building, a pilot study will begin in January 2019, and enroll 20 ASD caregiver-child dyads from culturally diverse, low-resource backgrounds.

The R21 will evaluate NDBI child, caregiver-child, and caregiver treatment targets, and a digital outcome measure of treatment response. The study design will include both a baseline cross-sectional phase and a longitudinal pre-post phase, nested within the ongoing K01. The R21 will extend ASD group recruitment by 1 year, allowing for 30 ASD caregiver-child dyads to be recruited in total. In addition, the R21 will facilitate recruitment of 30 children with developmental delay and 30 with typical development

who, along with the ASD group, will participate in the baseline cross-sectional phase of the study. The ASD group will then participate in the longitudinal pre-post phase of the study, where they will receive 12 NDBI-informed caregiver coaching sessions delivered by non-specialists.

COVID-19 adaptations: Transition to telehealth will only occur for the ASD group who receive the caregiver coaching intervention. Baseline assessments of the TD and DD group will be on hold until COVID-19 in-person restrictions are lifted by the University of Cape Town IRB.

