- Joint Engagement Rating Inventory (JERI): (Video recorded caregiver child interaction. Coded by trained coder) The Joint Engagement Rating Inventory (JERI) contains seventeen 7 point Likert scale items that characterize various aspects of joint engagement. The items span the range of possibilities observed during interactions with 18 to 30 month typically developing children and similarly aged and older children with developmental delay, including ASD. In order to assess joint engagement, a 10-minute video-recorded caregiver-child interaction will be scored in a Likert scale by a trained rater, blind to child diagnosis. Items focus on engagement states, child-specific codes, caregiver-specific codes, and shared topics. All individuals coding the JERI in this study will undergo reliability training involving dual coding of video-recorded caregiver-child interactions. Using Nvivo coding software, videos will be coded using the JERI coding manual. Nvivo coding software allows coder inconsistencies to be identified during reliability training so that each difference can be discussed until consensus is reached. This process will continue for each coder until 80% reliability is achieved. After training, 15% of JERI study data will be double coded to ensure maintenance of reliability. Adamson, L.B., et al., Rating parent-child interactions: joint engagement, communication dynamics, and shared topics in autism, Down syndrome, and typical development. *J Autism Dev Disord*, 2012. 42(12): p. 2622-35.
- Early Social Communication Scales (ESCS) (Completed by child, with support from clinician. Video recorded and coded by trained coder). Mundy, P., Delgado, C., Block, J., Venezia, A. and Siebert, J., 2003, Early Social Communication Scales (Coral Gables, FL: University of Miami). Joint

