- The Ten Questions Questionnaire (TQ) (Completed by caregiver) The Ten Questions Questionnaire (TQ) is a disability screening tool, extensively used in both epidemiological studies and clinically in low resource settings, including South Africa. The TQ consists of 10 questions; one each addressing the child's vision, hearing, movement and seizures, six on cognition competence, and one extra question regarding other serious health problems. Durkin, M.S., et al., Evaluating a ten questions screen for childhood disability: reliability and internal structure in different cultures. *J Clin Epidemiol*, 1995. 48(5): p. 657-66.
- Autism Behavior Checklist (ABC) (Completed by caregiver) The Autism Behavior Checklist (ABC) will be used to exclude autism spectrum disorder in the typically developing and developmental delay groups. The ABC is the most widely used screening tools for ASD in low and middle income countries; and the ABC age range aligns with our target recruitment age range. The ABC provides a checklist of 47 behaviors typical of autistic individuals for use during the initial screening process Krug, D., J. Arick, and P. Almond, *Autism Screening Instrument for Educational Planning* (3rd ed.). 2008, Austin, TX: Pro-Ed Copyrighted Instrument: <https://www.proedinc.com/Products/12742/asiep3-autism-behavior-checklist-record-forms-25.aspx>

- Griffiths Scales of Child Development, Third Edition (Griffiths III) – described in baseline assessments (ASD group)
- Joint Engagement Rating Inventory (JERI) – described in baseline assessments (ASD group)
- Early Social Communication Scales (ESCS) – described in baseline assessments (ASD group)
- SenseToKnow App – described in baseline assessments (ASD group)
- Technology Questionnaire and Qualitative Interview of SenseToKnow App feasibility/appropriateness
- In the longitudinal pre-post phase of the study all 30 ASD caregiver-child dyads will receive 12, 1-hour ESDM-informed caregiver coaching sessions delivered by non-specialist Early Childhood Development practitioners. The longitudinal phase has a single study arm, and all ASD caregiver-child dyads will receive the same assessments and the same intervention. The longitudinal pre-post phase of the study will be used to investigate the exploratory component of Aim 1: Changes in child treatment targets measured with SenseToKnow app; and Aim 3: Changes in caregiver strategies targeted by the intervention.

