Longitudinal pre-post phase assessments in the ASD group include:

- Caregiver Early Start Denver Model Implementation Fidelity: (Completed by clinician) Likert-based five-point rating system used to assess caregiver mastery of ESDM techniques S. Rogers, G. Dawson, L. Vismara, ESDM Parent Fidelity Tool (unpublished work). (2012).
- Non-Specialist Coaching Fidelity: (Completed by clinician) Likert-based four-point rating system used to assess therapist mastery of parent coaching techniques. S. Rogers, G. Dawson, L. Vismara, ESDM Parent Fidelity Tool (unpublished work). (2012).
- The Vineland Adaptive Behavior Scales, Third Edition (Vineland-3) – described in baseline assessments
- Griffiths Scales of Child Development, Third Edition (Griffiths III) – described in baseline assessments
- Caregiver competence: The Parent Sense of Competence Scale – described in baseline assessments
- Caregiver stress: The Parenting Stress Index – Short Form – described in baseline assessments
- SenseToKnow App – described in baseline assessments
- Joint Engagement Rating Inventory (JERI) – described in baseline assessments
- Qualitative Interview of Caregiver Strategies used during Caregiver-child Interactions (post-intervention in ASD group)

COVID-19 Adaptations: Remote follow-up assessments in the ASD group who will include the following approved measures from above: a, b, c, e, h, i. Note that a,b,h are coded by a trained coder from video-recorded caregiver child interactions. It would not be feasible to complete the full battery of measures remotely. We aim to evaluate implementation outcomes (acceptability, appropriateness,

feasibility) of the telehealth-delivered caregiver coaching approach. Acceptability, appropriateness, and feasibility will be quantitatively assessed using 4-item, pragmatic scales: The Acceptability of Intervention Measure (AIM), Intervention Appropriateness Measure (IAM), and Feasibility of Intervention Measure (FIM). Readability is at the 5th grade level. Higher scores indicate greater acceptability, appropriateness, and feasibility. In addition, acceptability, appropriateness and feasibility will be assessed qualitatively with stakeholder individual interviews. Questions in the interview guide will be tailored to stakeholder group and will be informed by previous studies that have examined implementation barriers and facilitators during the implementation of new treatment approach.

Specific Aims and Research Methodology

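### Aim 4 caregiver fidelity is a subjective video rating tested pre-post in a single arm, and the plan specifies no masking of raters to time point

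*Combined protocol and SAP*

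**What the plan says.** **Fidelity (Data Analysis & Statistical Considerations, Aim 4).** Thirteen items are rated 1 to 5 from smartphone video, "manually coded by certified ESDM therapists at baseline, for each of the 12 intervention sessions, and at follow up". Change in the telehealth group is tested with a paired t-test or a signed rank test, with 90% power claimed for a mean change of 0.5 at an SD of 0.6. The same section says "we expect that caregivers will learn to implement core NDBI intervention principles after 12 intervention sessions".

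**Who rates.** The list of longitudinal assessments under Design & Procedures marks the fidelity tool as completed by a clinician. The COVID-19 note below that list assigns the remote follow-up ratings to a trained coder. Aim 4 names certified ESDM therapists. Selection of Subjects describes three ESDM supervisors who are themselves trained ESDM therapists and oversee the coaching.

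**Design.** "The longitudinal phase has a single study arm, and all ASD caregiver-child dyads will receive the same assessments and the same intervention".

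**JERI (Aim 3).** Caregiver strategies are rated from video: "These items will be scored on a Likert scale by a trained rater, from video-recorded caregiver-child interactions". The longitudinal list carries the baseline description forward: "Joint Engagement Rating Inventory (JERI) – described in baseline assessments". That description has "a 10-minute video-recorded caregiver-child interaction will be scored in a Likert scale by a trained rater, blind to child diagnosis", and adds: "After training, 15% of JERI study data will be double coded to ensure maintenance of reliability". For remote work, "Transition to telehealth will only occur for the ASD group who receive the caregiver coaching intervention".

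Neither document section mentions masking to time point or a random scoring order for either tool. Double coding is specified for the JERI but not for fidelity.

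**The concern.** In a controlled trial, a rater who expects improvement and does not know the arm biases both arms alike. Here the contrast is time, and there is only one arm. If raters know which clip is baseline and which is follow-up, any leniency they share at follow-up goes wholly into the estimated change, and nothing in the analysis can separate it from learning. The plan expects improvement, the scale depends on judgement, and the raters are trained in the method being taught. Double coding would not remove the problem, because it detects disagreement between raters and not an expectation they hold in common.

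The fidelity test has its own 90% power statement, so it is meant to support inference as well as monitoring. A biased gain would also bear on the aim itself, because Aim 4 sets out to adapt the assessment of caregiver strategies for telehealth.

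**Working it through.** **Inputs from Aim 4 of the analysis section.** SD 0.6, design change 0.5, power 90%, pilot means 2.93 and 3.73 (gain 0.80, n=10). VABS-3: SDs 7.5 and 8.3, with detectable changes 5.7 and 6.3 at 90% power.

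**Assumptions.** Two-sided 5% test (alpha is not stated); 0.6 is the SD of change; rater shift b = 0.2 SD = 0.2 × 0.6 = 0.12 points. No document supports any particular b.

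**Step 1: the plan's own figures.** The telehealth n is not stated, so I solved for it. For a paired t-test the detectable change is d × SD, where d gives 90% power at that n.

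| n | d | Socialization (7.5d) | Communication (8.3d) | Fidelity (0.6d) |
|---|---|---|---|---|
| 19 | 0.787 | 5.90 | 6.53 | 0.472 |
| 20 | 0.7645 | 5.73 | 6.345 | 0.459 |
| 21 | 0.744 | 5.58 | 6.175 | 0.446 |
| Stated | | 5.7 | 6.3 | 0.5 |

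Only n=20 matches both VABS-3 figures, and 0.459 rounds to the stated 0.5. I use n=20.

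**Step 2: rejection probability with a shift.** P(|T| > 2.093), where T is noncentral t with 19 df and noncentrality √20 × (true change + b)/0.6.

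| True change | Noncentrality, b=0 | Rejects, b=0 | Noncentrality, b=0.12 | Rejects, b=0.12 |
|---|---|---|---|---|
| 0 | 0 | 5% | 0.894 | 13.6% |
| 0.2 | 1.491 | 29.4% | 2.385 | 61.9% |
| 0.5 (design) | 3.727 | 94.2% | 4.621 | 99.2% |

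At zero true change, other shifts give 7.1% (0.1 SD) and 24.7% (0.3 SD).

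**Step 3: effect on the estimate.** At a true change of 0.5, the expected estimate is 0.62, which overstates the change by 0.12/0.5 = 24%. If a gain of 0.80, as in the pilot, included the shift, the shift would be 0.12/0.80 = 15% of it. The remaining 0.68 would still be detected with 99.8% power.

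**Step 4: if 0.6 is the SD at one time point.** The SD of change is then 0.6 × √(2(1−r)). With r = 0.3, 0.5 and 0.7, a 0.12-point shift at zero true change rejects 11.1%, 13.6% and 19.5% of the time.

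**Step 5: the JERI.** Aim 3 has n=30. If all 30 dyads shifted by 0.2 SD with zero true change, rejection would be 18.5%. If only remote dyads shifted, the mean shift would be smaller. With 20 of 30 remote (assumed), it is 0.2 × 20/30 = 0.133 SD and rejection is 10.9%. With 10 remote, it is 0.067 SD and 6.4%.

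**The case against.** The strongest reply is that the documents are silent. They do not say that raters know the time point. A reader might infer that the coaching supervisors score their own dyads, because both groups are ESDM therapists. The text does not say so, and the trained coder named for remote follow-up may be a different person. That objection stands: the supportable statement is that masking and separation are not specified, and that the descriptions of the rater need reconciling.

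A reader might also take the JERI test in Aim 3 to be equally exposed. The documents do not support that for in-person clips. The blind to diagnosis carries to follow-up, and only ASD dyads have a follow-up, so telling a rater that a clip is a follow-up would reveal the diagnosis. Keeping the stated blind therefore already requires withholding that label. For remote clips this protection falls away, because only the ASD group moved to telehealth. Baseline and follow-up clips are both smartphone recordings there, so format alone does not reveal time point; labels and scoring order are what remain open.

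Third, the shift is assumed, and at the plan's design value it barely changes the test. That also stands. It limits the harm to an inflated estimate and to the case of a small true change; it does not remove it.

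Finally, Aim 4 is exploratory, and the analysis section promises caution with pre-post inference for Aim 3. Caution in interpretation does not correct a biased rating.

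**Conclusion.** The gap is real for Aim 4 fidelity: a judgement scale, a single ASD-only arm, a stated expectation of improvement, and no specified masking to time point, scoring order or separation from the coaching team. At the design change its main consequence is an overstated gain. A material false-positive risk arises only if the true telehealth change is small. The sizes rest on an assumed 0.2 SD shift, an implied n of about 20, a two-sided 5% test, and 0.6 being the SD of change.

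A reader might infer that a significant fidelity gain would be spurious, or that the pilot gain was. The figures do not support that: a gain of pilot size would survive removal of a 0.12-point shift. Nor is the main Aim 1 analysis in question. Its three co-primary comparisons contrast diagnostic groups, with an examiner or rater blind to diagnosis.

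The JERI part is limited to remote ASD clips. Severity is low to moderate, because these are secondary or exploratory tests.

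**What to change.** **Fidelity.** For the pre-post test only, give baseline and follow-up clips random IDs, remove dates and session labels, and shuffle them across dyads and time points. The existing certified therapists can score them. Where possible, each dyad should go to a therapist who did not coach it, supervise it or rate its session clips. Keep the session-by-session ratings for monitoring only. State who rates, so that the clinician, the trained coder and the certified therapist are reconciled, and state the telehealth n and alpha.

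**JERI.** Apply the same IDs and shuffling to remote ASD clips. Keep the DD and TD clips in the scoring pool, so that ASD clips are not set apart and the blind for the Aim 1 joint-engagement endpoint is not weakened.

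**Cost.** No new visits, recordings or coders. For fidelity, either outcome scoring waits until follow-up, or about 20 baseline clips are scored again. Against 20 × 14 = 280 planned ratings, that is 20/280 = 7% more. The Background calls skilled fidelity raters a limited resource, which is why the reassignment is only where possible. For the JERI, holding baseline clips back would delay the Aim 1 and Aim 2 results that use them, so the scoring schedule should be set with that in mind.

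**Limits.** Masking will be partial, because coached behaviour may be visible on the clip. It does not remove maturation or regression to the mean, so the result should still be reported as change and not as an effect of coaching.
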